PROSPECTIVE STUDY OF
PULMONARY COMPLICATIONS OF
HUMAN IMMUNODEFICIENCY VIRUS INFECTION

P R O T O C O L

February 25, 1991

Prospective Study of
Pulmonary Complications of Human
Immunodeficiency Virus Infection

Protocol Summary

This study seeks to provide information concerning the pulmonary diseases that occur as a result of infection with the human immunodeficiency virus (HIV). The primary objective of the study is to determine the frequency and types of lung diseases that occur in persons with HIV infection and to describe the course and outcome of these disorders. These diseases or abnormalities may be either secondary to the immunologic abnormalities caused by the virus (opportunistic processes) or the result of the HIV infection itself.

The study will be based in seven Clinical Centers (six in the United States and one in Europe) and will be a prospective, longitudinal evaluation of a cohort of seropositive persons and seronegative control subjects. Seropositive subjects will be stratified into two groups defined by the number of circulating CD-4 cells (≥ 400 per microliter, < 400 per microliter) and the presence or absence of "pre-AIDS" conditions. Evaluations of these three groups will enable identification of the lung diseases that occur at various stages of HIV disease. The "background" prevalence/incidence of various diseases and abnormalities that are related to demographic, environmental, or lifestyle factors, rather than HIV infection, will be determined by evaluation of the seronegative group.

Evaluations will be conducted at regular intervals and when predefined symptoms occur. Screening and diagnostic studies that are of proven value in detecting AIDS-associated lung diseases will be used. Tests will be performed in a uniform manner using standardized techniques among all Clinical Centers. Subjects will be followed for between 3 and 4 years (one year recruitment period and 3 year period of observation) or until death.

As a substudy, the effect of early detection of P. carinii pneumonia on subsequent morbidity and mortality will be evaluated. Seropositive subjects will be allocated at random to either "routine" (testing at 12-

month intervals) or "intensive" (testing at 3-month intervals) evaluations.

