3.1 Natural history of HIV infection

Substantial evidence now suggests that HIV infection is persistent and generally progressive, producing clinical illness (AIDS or AIDS-related conditions-ARC) in at least a majority of seropositive persons within five years from the time of seroconversion (1). Reported rates of progression to AIDS have been variable. In the San Francisco City cohort 30% of seropositive homosexual or bisexual men developed AIDS at a median of 5 years from the time of seroconversion (1). Goedert and coworkers (2) showed 3 year actuarial progression rates of 34% and 17% in cohorts of homosexual men in New York and Washington whereas Polk and associates (3) reported a crude 15 month progression rate of only 3.2% in a multicenter study of homosexual and bisexual men. One cohort of hemophiliacs showed an 18% rate of progression at 6 years after seroconversion (4). More recently, Moss and associates (5) reported a 3 year actuarial progression rate to AIDS of 22% with an additional 19% developing ARC.

Data from several of these same studies describe indicators that serve to predict the risk of progression to AIDS and, thus, are markers for the stage of HIV disease. In all studies a lower number of circulating CD-4 lymphocytes on enrollment was correlated with an increased rate of developing AIDS. Additionally, a progressive reduction in CD-4 cells was highly associated with the risk of AIDS. Direct relationships with risk of AIDS have been found with beta 2

microglobulin concentration and HIV P-24 antigenemia, and inverse relationships detected with the level of HIV antibody, hemoglobin concentration, and platelet count (3,4,5,6,7). Clinical predictors of progression have also been identified and include the presence of thrush (oral candidiasis) hairy leukoplakia, constitutional symptoms (unexplained fever and weight loss) and persistent unexplained diarrhea.

Particularly noteworthy were the findings by Moss and associates (5) that in the men in their cohort who did not develop AIDS or ARC there, nevertheless, was a progressive decrease in the absolute number of CD-4 cells during the 3 year period of observation. The median CD-4 counts in this subgroup fell from a baseline value of 626 to 428 cells per microliter at the end of 3 years in rather even decrements of approximately 65 to 70 cells per year. This observation is indicative of the chronic progressive nature of HIV disease during a time when it is subclinical.

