This study is designed to identify the lung diseases that occur in patients with all stages of HIV infection and to describe the "natural history" of these processes. Patients will be managed with current standard or approved experimental care, thus, the course described will be that of the treated process, not the true natural history. To accomplish this objective a cohort of subjects with HIV infection and an HIV seronegative control group will be prospectively evaluated in six centers in the United States and one in Europe. Seropositive study subjects will be stratified into two groups: Group A subjects will consist of persons who have not had symptoms or diseases likely to be associated with HIV infection as specified in Table 2 and will have ≥ 400 CD-4 cells per microliter; Group B subjects will be identified by having either clinical findings or < 400 CD-4 cells per microliter or both. Seronegative control subjects (Group C) will be enrolled concurrently. Screening and diagnostic studies will be applied in a uniform fashion at predetermined intervals, and when symptoms or findings suggestive of lung disease are noted. Each subject will be followed for between three and four years (depending on date of entry) or until death and data describing the course and outcome of pulmonary processes will be collected over the full duration of the study. All data will be collected on standard forms and will be transmitted to the Coordinating Center (CC) where studywide computer files will be maintained.

[figure not shown]
Stratification of seropositive study subjects by level of CD-4 cells and the presence or absence of HIV-related clinical manifestations will provide a spectrum of severity of HIV infection and consequently lower and higher risks of developing HIV-related lung diseases. It is anticipated that Group A subjects will be more likely to manifest pulmonary disorders that do not serve to define AIDS (Table 1), that occur earlier in the course of HIV infection, and that may be underappreciated by most clinicians. Examples include pyogenic bacterial pneumonias and tuberculosis. In addition, it is primarily in this group that evidence of lung disease that might be caused by HIV itself will be sought.

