7.2.3 Scheduled follow-up evaluations

Table 6 shows the evaluations to be performed and their frequencies in each of the groups. During these evaluations a modified history and physical examination will be done and the same series of laboratory tests as performed in the initial evaluation (except induced sputums) will be obtained. For purposes of data analysis subjects will be considered as belonging to the group to which they were originally assigned. Subjects in Groups A-1, B-1 and C who develop an HIV-related pulmonary process will continue to be followed at the same intervals except that pulmonary function tests will be performed every 6 months. HIV seronegative controls (Group C) will be followed at the same intervals as Groups A-1 and B-1. The schedule for Group C subjects who become HIV seropositive will not change.

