7.2.4 Diagnostic evaluation of symptoms or findings suggestive of lung disease

All diagnostic evaluations will be performed in the Clinical Centers and will follow the algorithms devised for purposes of the protocol (Section 7.2.7). The diagnostic evaluation may be triggered by the occurrence of symptoms (noted either at the time of a scheduled evaluation or between evaluations) or by chest radiograph detected on scheduled screening examinations. Standard methods to be used for each of the studies are described in Appendix 5. All data will be recorded on standard forms.

The symptoms that will trigger an evaluation include:

Table 6
Schedule of Interval Laboratory Studies

Frequency of studies (months)
(See text for definitions of group)

Study	Group A-1(1)	Group A-2	Group B-1(1)	Group B-2	Group C(1)	1-month F/U (all groups)(2)
History Performance status	6	3	6	3	6	+
Physical Exam	6	3	6	3	6	+
CBC/Diff, platelets	6	3	6	3	6	+
ESR/SMA	6	3	6	3	6	+
Absolute CD-4 CD-8, CD-3(4)	6	3	6	3	6	+
Serum Bank	6	3	6	3	6	+
HIV Ab(3)	Entry	Entry	Entry	Entry	6	0
Induced Sputum	Entry	Entry	Entry	Entry		
Skin tests	12	12	12	12	12	0
PFT	12	3	12	3	12	+
CXR (PA/Lat)	12	3	12	3	12	+

(1) Subjects enrolled in Group A-1 or B-1 who later develop an HIV-related pulmonary complication will continue the same schedule, except PFT's will be performed every 6 months. The schedule of evaluations for Group C subjects who seroconvert will not change.

(2) "+" = test performed.

(3) Omit if documented positive prior to study entry.

(4) May be omitted if performed within the three months prior to visit.

1) unexplained cough that persists for more than five days;
2) unexplained breathlessness (progressive over ≥ 5 days or severe ≥ 1 day); or 3) unexplained new onset of documented fever ($\geq 38^{\circ}\text{C}$ oral ≥ 5 days). As a part of the orientation and at each routine clinic visit, each study subject will be alerted to these symptoms and instructed to contact the study office should they develop. For each of these symptoms, if a reason other than a possible HIV-related pulmonary process can be found (e.g., asthma), the evaluation will not proceed. If the subject has fever with localizing extrapulmonary symptoms (e.g., diarrhea) and no pulmonary symptoms, the evaluation will not proceed, and the subject will be referred to the primary physician. Any diagnoses resulting from such an episode will be entered at the subsequent visit on the Interval Visit Questionnaire.

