- 5) Selected physicians providing primary care to a large number of HIV-infected patients in Frankfurt will be approached and invited to refer their patients for regular pulmonary work-ups in our department.

In case the number of participants recruited from PACS from these sources during the first 3 months of the study is less than required, we intend to publish the aims of this study in regional newspapers and on radio and TV inviting potential participants to join the study.

Individuals for Group C (control) will be recruited from a cohort of non-infected sexual partners of HIV patients currently studied at Frankfurt University Hospital. A special effort is made to recruit HIV seronegative IV drug abusers who are treated in the emergency room of Frankfurt University Hospital.

Appendix 5

Procedures

Pulmonary Complications of HIV Infection

Manual for Diagnostic Procedures,
Specimen Collection and Processing

PULMONARY COMPLICATIONS OF HIV INFECTION
DIAGNOSTIC SPECIMEN PROCESSING

I. Routine Studies

- A. Sputum Collection -- induced with ultrasonic nebulizer (USN)
 - 1) Stains: P. carinii, (Giemsa, silver, toluidine blue, DFA), acid fast, papanicolaou, CMV DNA probe - optional)
 - 2) Cultures: mycobacterial (viral, fungal - optional)
- B. Bronchoscopy -- Bronchoalveolar lavage -- optional
 - 1) Stains: P. carinii (Giemsa, silver, toluidine blue) acid fast, papanicolaou (CMV DNA probe - optional)
 - 2) Cultures: mycobacterial, fungal, viral

II. Diagnostic Evaluations

- A. Sputum Collection
 - 1) Spontaneous:
 - a) Stains: Gram's, acid fast
 - b) Cultures: bacterial, mycobacterial, fungal
 - 2) Induced with USN
 - a) Stains: P. carinii (Giemsa, silver, toluidine blue), acid fast, papanicolaou, CMV DNA probe, Legionella DFA or Probe, Mycoplasma Probe (e.g., all but Giemsa, Acid Fast - optional)
 - b) Cultures: mycobacterial, fungal (viral, Legionella, Mycoplasma - optional)
- B. Bronchoscopy
 - 1) Bronchoalveolar Lavage
 - a) Stains: P. carinii (Giemsa, silver, toluidine blue), acid fast, (Papanicolaou, Legionella, DFA, CMV DNA Probe, Legionella Probe, Mycoplasma Probe - optional)
 - b) Cultures: mycobacterial, fungal (viral, Legionella, Mycoplasma - optional)
 - 2) Transbronchial Biopsy
 - a) Stains: Silver, Acid Fast, Hematoxylin and Eosin
 - b) Touchprep: (Giemsa, silver, toluidine blue - optional)
 - c) Cultures: (mycobacterial, fungal - optional)
 - 3) Transbronchial Needle Aspiration
 - a) Stains: Papanicolaou, Silver, Acid Fast

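### The unrestricted original-group rule in Section 7.2.3 keeps Group C seroconverters as seronegative controls and makes Group A and B rates entry-stage rates; it should be limited to the randomised comparison and to rates labelled by entry stage

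*Protocol*

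**What the plan says.** The rule stands in Section 7.2.3: "For purposes of data analysis subjects will be considered as belonging to the group to which they were originally assigned". It is not confined to the routine/intensive arms. The same paragraph deals with Groups A-1, B-1 and C, and Figure 1 in Section 5 uses the term group assignments for the whole design.

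The paragraph also foresees seroconversion, but settles only the visits: "The schedule for Group C subjects who become HIV seropositive will not change". Table 6 repeats the HIV antibody test every 6 months in Group C (row "HIV Ab(3) Entry Entry Entry Entry 6 0"). Nothing in the protocol ends or reclassifies a seroconverter's control follow-up.

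On what the groups are for, the Protocol Summary says: "Evaluations of these three groups will enable identification of the lung diseases that occur at various stages of HIV disease". Section 5 adds that evidence of disease caused by HIV itself will be sought mainly in Group A.

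In Appendix 1, Question 1 lists HIV antibody status and stage of infection as predictors, and Questions 9 and 10 list HIV status. None says whether this means status at entry or current status. The Appendix 1 introduction counts a disease as HIV-associated if it is seen only in seropositives, or significantly more often in them. Question 8 uses measured CD4 with models suited to time-dependent covariates. Section 8.9 has the Coordinating Center monitor movement between categories, but ties this to no analysis.

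**The concern.** Keeping subjects where they were randomised protects the comparison of A-1 with A-2 and B-1 with B-2. Groups A, B and C themselves are not randomised. They are states of infection that can change over the planned follow-up: "Each subject will be followed for between three and four years (depending on date of entry) or until death".

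Two things follow from applying the rule to them.

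- **Controls.** HIV-related events, symptoms or lung-function loss in a seroconverter would count towards the background rate. Under the criterion that a disease occurs only in seropositives, one such event is enough to break the test. The precision calculations in Appendix 3 assume a Group C rate of 0% for *P. carinii* pneumonia, so a few events would be visible. At Frankfurt the exposure is explicit: "Individuals for Group C (control) will be recruited from a cohort of non-infected sexual partners of HIV patients".
- **Stage.** A Group A rate becomes the rate in people who entered with at least 400 CD4 cells and no manifestations. It is not the rate while people are in that state. Presented without that label, later-stage disease could be read as early-stage disease.

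**Working it through.** **1. The plan's own figures.** Half-width = 1.96 × √(p(1−p)/n), with n = 527 in each of A and B (Table 5B) and one-year rates of 5% and 20% (Appendix 3).

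- A: 1.96 × √(0.05 × 0.95/527) = 0.019 (stated 0.02)
- B: 1.96 × √(0.20 × 0.80/527) = 0.034 (stated 0.03)
- A versus B: 1.96 × √((0.05 × 0.95 + 0.20 × 0.80)/527) = 0.039 (stated 0.04)

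These reproduce. They are calculated by entry group for one year of follow-up.

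**2. Movement out of Group A.** Section 3.1 reports on seropositive men who did not develop AIDS or ARC: "The median CD-4 counts in this subgroup fell from a baseline value of 626 to 428 cells per microliter" over 3 years. The slope is (626 − 428)/3 = 66 cells a year; the text says 65 to 70. The spread of entry CD4 is not given, so it is assumed.

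Take entry CD4 as lognormal with median 626 and log-SD s, truncated at 400. With decline d a year, the share below 400 at time t is [F(400 + d·t) − F(400)] / [1 − F(400)].

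Example with s = 0.35, d = 66, t = 3, so 400 + 198 = 598:

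- F(598) = Φ(ln(598/626)/0.35) = Φ(−0.131) = 0.448
- F(400) = Φ(ln(400/626)/0.35) = Φ(−1.280) = 0.100
- Share = (0.448 − 0.100)/0.900 = 0.386

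| Assumption | Below 400 at 1 year | Below 400 at 3 years |
|---|---|---|
| Lognormal, s = 0.25-0.45, d = 65-70 | 8-12% | 35-44% |
| 400 + gamma excess, median 626, SD 150-250, d = 66 with between-subject SD 0 or 40 | 5-14% | 41-45% |

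Under the lognormal assumption, 20-23% of Group A person-time over 3.5 years (the midpoint of 3 to 4) is below 400.

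**3. Seroconversion in Group C.** The rate r is not in the protocol; 1-5% a year is assumed, with T = 3.5 years and 177 controls (Table 5B).

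- Seroconverters = 177 × (1 − e^(−rT)). At 1%: 177 × 0.034 = 6. At 5%: 177 × 0.161 = 28.
- Infected share of follow-up = 1 − (1 − e^(−rT))/(rT). At 1%: 1.7%. At 5%: 8.3%.

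An HIV-versus-control contrast shrinks by at most about that share. The DLCO difference of 0.8 for intravenous drug users in the Appendix 3 text would be seen as 0.8 × 0.983 = 0.79 down to 0.8 × 0.917 = 0.73.

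For a disease with no expected control cases, control follow-up is 177 × 3.5 = 619.5 person-years, of which 10.5 to 51.4 would be infected (1.7% and 8.3%). If the 5% annual rate applied there, 0.5 to 2.6 events would fall in Group C. This is an upper illustration, because recent seroconverters are early in infection and Section 1 describes several years of latency.

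**The case against.** The rule follows directly on Section 7.2.2, which describes randomisation, so it can be read as an intention-to-treat statement only. The analytic plans are in Appendix 1, which names measured status rather than group labels. Question 8, the question about CD4 stage, already uses time-dependent CD4. Rates by entry group are a legitimate prognostic estimate, and Section 5 describes the strata as giving lower and higher risk. All of this stands, and it narrows the point. It does not remove it: the sentence is unlimited, and where Questions 1, 9 and 10 leave entry or current status open, the only rule that settles the matter settles it as entry.

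A reader might infer more: that combining the 5% and 20% planning rates with the time spent below 400 shows a large part of Group A's events to be later-stage disease, and the Group A rate to be well above 5%. The documents do not support this. Section 7.1.4 attaches 5% per year of observation to people with more than 400 cells, which reads as a rate by entry class that already includes later decliners. It ties the 20% to more severe immunosuppression, not to anyone just under 400. Nor does a falling median mean that each subject entering between 400 and 600 crosses the threshold. The stated half-widths are for one year, when few would have crossed.

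A reader might also infer serious dilution of every control comparison. On the assumed rates the average effect is small. The Frankfurt source concerns a center with a Group C quota of 30, and that center also seeks seronegative drug users.

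Making current A/B status the primary analysis would bring its own bias. Group B signs such as prolonged fever and weight loss may be early symptoms of the lung disease being counted, and status is updated every 3 months in one arm and every 6 in the other.

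**Conclusion.** The point holds in limited form. Section 7.2.3 applies a rule suited to the randomised arms to all groups. Read literally, it conflicts with the HIV-status comparisons in Questions 1, 9 and 10 and with the Appendix 1 criterion for an HIV-associated disease. For Groups A and B it yields entry-stage rates, which are valid if labelled so, but are not rates by current stage.

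The stage movement (35-45% of Group A below 400 at 3 years) rests on the protocol's decline and an assumed baseline spread. The control effect (6-28 of 177 subjects, 2-8% of follow-up) rests wholly on an assumed seroconversion rate. It is modest on average; the exposed place is a rare disease with an expected control rate near zero. The stage question as such is not lost, because Question 8 is planned on measured CD4.

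**What to change.** 1. In Section 7.2.3, limit the original-group rule to the randomised intensive/routine comparison (Questions 12-14) and to rates labelled as by entry stage.
2. For Questions 1, 9 and 10, end a Group C subject's seronegative follow-up at the last negative antibody test. Analyse later follow-up separately or as seropositive.
3. Keep the Group A and B rates by entry group, with that label.
4. Add a supporting table of events and person-time by current CD4, consistent with Question 8. Use a CD4 value lagged before the event and the same update interval in both arms; the 6-month values exist in both.

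The cost is some programming and slightly fewer seronegative person-years (2-8% on the assumed rates). No new data are needed: Group C antibody is tested every 6 months and CD4 every 3 or 6 months under Table 6.

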there may be pulmonary involvement, either primary or secondary, at any point in the course of HIV disease. Although much is known about the pulmonary disorders associated with AIDS, there are very important deficiencies in the available information. These deficiencies are due in large part to clinicians and investigators focusing on those disorders that serve to define AIDS or that occur in patients who have AIDS. There is little or no information that systematically identifies the pulmonary disorders that occur at all stages of HIV disease or that describes the course patients follow after the diagnosis of a lung disease has been established.

2. Primary and Secondary Objectives

The primary objective of this study is to determine the prevalence, incidence, and types of lung diseases that occur in persons in selected HIV transmission categories with and without HIV infection and to describe the course and outcome of these disorders.

Within the context of the primary objective there are several secondary objectives that this study seeks to achieve. These are subsidiary to the primary objective but have importance in their own right.

The secondary objectives are as follows:

1. To identify demographic, clinical, and immunologic and other laboratory variables that are associated with the subsequent diagnosis of specific HIV-related lung diseases;
2. To describe the clinical, radiographic, and pulmonary physiologic, immunologic, and other laboratory variables that are associated with specific HIV-related lung diseases at the time the disease is diagnosed;
3. To determine if there is a difference in the prevalence/incidence of identified pulmonary disease, respiratory symptoms, chest radiographic abnormalities, and rates of decline in pulmonary function in subjects with HIV infection compared with these same variables in subjects from the same HIV transmission categories who do not have HIV infection;

4. To measure the frequency with which HIV-related lung diseases are present in HIV-infected persons who do not have symptoms;
5. To compare survival, days in hospital and functional status in subjects who have had lung diseases diagnosed as a result of intensive screening or evaluation of respiratory symptoms with subjects who have had the same diseases diagnosed as a result of routine screening tests or evaluation of respiratory symptoms.

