Group B subjects, as indicated by their having clinical or laboratory findings indicative of more severe immunosuppression (Table 2), will be at greater risk of developing HIV-associated, often AIDS-defining, lung diseases. It is anticipated that studies of individuals in Group B will serve to determine the natural history of the AIDS-defining processes and to describe the diagnostic features of second and subsequent episodes of P. carinii pneumonia. Because it is estimated (from the data of Moss et al) that approximately 5% of Group A and 20% of Group B patients will develop an AIDS-defining condition each year, in most instances P. carinii pneumonia, a specific group of subjects with existing AIDS will not be recruited.

Inclusion of an HIV-seronegative control group will be necessary to determine if diseases and abnormalities in pulmonary function that are anticipated in Groups A and B are related to the HIV infection or may be caused by lifestyle or other factors independent of HIV infection. Group C will be composed of homosexual/bisexual men and intravenous drug users and will be matched by age, race, and sex with Groups A and B. Homogeneity of transmission group distribution and matching characteristics between Group C and Groups A and B will be continuously monitored by the Coordinating Center with appropriate feedback to the Clinical Centers.

To determine the feasibility and impact of early diagnosis of P. carinii pneumonia subjects in Groups A and B will be assigned at random to equal size groups for either "intensive" (3 month intervals) or "routine" (12 month intervals) testing. Figure 1 describes the group assignments and follow-up intervals.

Figure 1
Group Assignments and Follow-up

(1) Intensive evaluation with history, physical examination and testing every 3 months.

(2) Routine evaluation with history and physical examination every six months and testing every 12 months. (See Table 6 for list of tests.)

Definition of Study Groups

- Group A: HIV seropositive. No symptoms or findings attributable to HIV. CD-4 cells \geq 400 per microliter.
- Group B: HIV seropositive. Either clinical manifestations attributable to HIV within the past 6 months (thrush, hairy leukoplakia, fever $>38^{\circ}$ C persisting > 2 weeks, involuntary weight loss $> 10\%$ of baseline, or diarrhea persisting >1 month) or CD-4 cells < 400 /microliter or both.
- Group C: HIV seronegative homosexual/bisexual men or intravenous drug users.

6. Anticipated Problems

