All HIV seropositive subjects

Predictive variables

Absolute and relative numbers of CD4 cells. The CD4 cells will be grouped into 3 categories (>399, 200-399, <200) in some analyses.

Confounding variables

Antiviral therapy

Preventive therapy for HIV-related lung diseases

Outcome variables

Specific HIV-related lung diseases

Analysis

Regression models, appropriate when time dependant covariates are present, will be used to study this question.

Question 9. Do HIV infected persons who have not had lung diseases diagnosed have a greater incidence/prevalence of respiratory symptoms, pulmonary function abnormalities and unexplained radiographic findings than HIV seronegative subjects in the same transmission category?

Groups studied

All HIV seropositive and seronegative subjects

Predictive variables

HIV status

Transmission category

Confounding variables

Previous or current lung disease (recognized HIV-related or nonHIV- related)

Smoking

Outcome variables

Symptoms

Vital capacity, total lung capacity, forced expiratory volume in one second, diffusing capacity

Radiographic findings

Analysis

Analytic strategies involving regression models (linear and logistic) will be used

Question 10. Does pulmonary function deteriorate more rapidly in HIV infected persons who have not had lung diseases diagnosed compared with HIV seronegative subjects in the same transmission category?

Groups studied

All HIV seropositive and seronegative subjects

Predictive variables

HIV status

Transmission category

Confounding variables

Previous or current lung disease (recognized HIV-related or nonHIV-related)

Smoking

Outcome variables

Changes in vital capacity, total lung capacity, forced expiratory volume in one second, diffusing capacity over time

Analysis

Regression models will be used to address these questions.

Appropriate measures of decline (change) in lung function measurements will be used as outcome variables

Precision

Half-width 95% confidence intervals of DLCO for A versus C and B versus C are 2.0 for IV drug users and 1.3 for gays.

Question 11. How sensitive are symptoms for specific HIV-related lung diseases?

Groups studied

All HIV seropositive and seronegative subjects

Predictive variables

Fever (> 38R oral for > 5 days)

Cough (with or without sputum for > 5 days)

Shortness of breath (mild to moderate > 5 days, severe > 1 day)

Confounding variables

Preexisting lung disease

NonHIV-related lung diseases

Outcome variables

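### Pooling 3-monthly-tested with yearly-tested seropositives against yearly-tested Group C can create an HIV excess in the incidence of silent or short-lived film and lung-function findings

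*Protocol*

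**What the plan says.** Section 5 says that "subjects in Groups A and B will be assigned at random to equal size groups". Figure 1 defines the two schedules: "Intensive evaluation with history, physical examination and testing every 3 months" for A-2 and B-2, and "Routine evaluation with history and physical examination every six months and testing every 12 months" for A-1 and B-1. Table 6 gives the detail. Chest films and lung function tests are 3-monthly in A-2 and B-2 and 12-monthly in A-1, B-1 and C; history and physical examination are 3-monthly against 6-monthly. Section 7.2.3 places the controls on the routine schedule: "HIV seronegative controls (Group C) will be followed at the same intervals as Groups A-1 and B-1".

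The comparisons with Group C do not follow that split.

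- Secondary objective 3 reads "To determine if there is a difference in the prevalence/incidence of identified pulmonary disease, respiratory symptoms, chest radiographic abnormalities", and goes on to rates of decline in lung function.
- In Appendix 1, the groups studied in Questions 9 and 10 are "All HIV seropositive and seronegative subjects". The listed confounders are "Previous or current lung disease (recognized HIV-related or nonHIV- related") and smoking.
- Question 1 studies all seropositives and treats a disease as HIV-related if it occurs only in them, or at a significantly higher rate than in seronegatives. Its listed confounders are treatments.

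Under Section 7.2.4 a radiographic abnormality on a scheduled film can start a diagnostic work-up, including in a subject without symptoms. Section 7.2.3 also says "For purposes of data analysis subjects will be considered as belonging to the group to which they were originally assigned".

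**The concern.** A silent abnormality that comes and goes is more likely to be caught by twelve films in three years than by three. When half of one side of a comparison has the denser schedule and none of the other side does, the proportion ever found abnormal, or the count of new findings, rises on the first side even if the underlying rates are equal.

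Two uses of the data are exposed. One is the incidence part of Question 9 and of secondary objective 3, for radiographic and lung-function abnormalities. The other is the Question 1 rule for calling a disease HIV-related, so far as the disease was found only because a scheduled film prompted a work-up. The excess would be credited to HIV when its source is surveillance. The randomised substudy itself rests on the idea that 3-monthly testing can find disease that yearly testing finds later.

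**Working it through.** **1. Does the plan pool the two schedules?** Inputs: Table 5B (A 527, B 527, C 177) and the Appendix 3 assumption of one-year PCP rates of 5%, 20% and 0%. Half-width = 1.96 × √[p₁(1−p₁)/n₁ + p₂(1−p₂)/n₂].

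- A versus C: 1.96 × √(0.05×0.95/527 + 0) = 0.019; Table 3.2 gives 0.02.
- B versus C: 1.96 × √(0.20×0.80/527 + 0) = 0.034; Table 3.2 gives 0.03.

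With A-1 or B-1 alone (n = 263.5) the results would be 0.026 and 0.048, which round to 0.03 and 0.05. The plan's precision figures therefore use the full pooled groups.

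**2. Finding of limited duration, seen only on a scheduled film.** A finding lasting d months is caught with probability min(1, d/3) on the 3-monthly schedule and min(1, d/12) on the 12-monthly one. Seropositives are split 1:1, so with equal true rates the apparent ratio is [½ min(1, d/3) + ½ min(1, d/12)] / min(1, d/12).

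| d (months) | 3-monthly | 12-monthly | Ratio, pooled to C |
|---|---|---|---|
| 3 | 1 | 0.25 | 2.5 |
| 6 | 1 | 0.50 | 1.5 |
| 12 or more | 1 | 1 | 1.0 |

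For d below 3 the ratio stays at 2.5 (for example d = 1: ½(0.333 + 0.083)/0.083).

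**3. Ever-found measure over three years.** Assumption, not in the protocol: each scheduled test shows the finding with probability p, the same in both HIV groups and independent between tests. This is the short-duration case. P(ever found) = 1 − (1−p)^k, with k = 3 yearly or k = 12 quarterly follow-up tests; the seropositive figure is the mean of the two. The last column is the chance of a significant seropositive excess (two-sided 5% two-proportion test with pooled null variance, 1,054 against 177).

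| p | Seropositive, pooled | Group C | Ratio | Falsely significant |
|---|---|---|---|---|
| 0.5% | 3.7% | 1.5% | 2.5 | 26% |
| 1% | 7.2% | 3.0% | 2.4 | 57% |
| 2% | 13.7% | 5.9% | 2.3 | 89% |
| 5% | 30.1% | 14.3% | 2.1 | 99.8% |
| 10% | 49.4% | 27.1% | 1.8 | >99.9% |

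At p = 1%: 1 − 0.99³ = 3.0%; 1 − 0.99¹² = 11.4%; mean 7.2%.

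**4. Rates of decline (Question 10).** Least-squares slopes were simulated under no HIV effect, with 527 subjects tested quarterly plus 527 tested yearly against 177 tested yearly (assumed mean slope −0.3, slope SD 0.5, measurement SD 1.5; 4,000 runs). The mean difference was 0.000 and the rejection rate 4.9%. Extra tests change the precision of a slope, not its mean.

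**5. Price of restricting to A-1 and B-1.**

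- DLCO (SD 2.5), A versus C: 1.96 × 2.5 × √(1/n₁ + 1/n₂). For homosexual/bisexual men, 356 against 124 gives 0.51, and 178 against 124 gives 0.57 (12% wider). For IV drug users, 136 against 53 gives 0.79, and 68 against 53 gives 0.90 (13% wider). The pooled values match the 0.5 and 0.8 in the Appendix 3 text; the 1.3 and 2.0 in Table 3.5 do not follow from an SD of 2.5 and are a separate matter.
- All seropositives against C: √(1/527 + 1/177) / √(1/1054 + 1/177) = 1.07.
- PCP: with 0% assumed in C, all the variance comes from the seropositives, so halving them widens the interval by √2 = 1.41 (0.019 to 0.026 in A; 0.034 to 0.048 in B).

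**The case against.** The strongest reply is that the matched comparison is already built in. Group C was put on the A-1/B-1 schedule, Appendix 1 declares its lists non-exhaustive, Section 9 calls for adjustment where risk variables are imbalanced, and a schedule term or choice of visits could sit in an analysis plan. Part of this stands: the absence of testing frequency from the confounder lists is weak evidence by itself. It does not rescue the comparison, because the population is fixed as all seropositives. Appendix 1 also names the one unlisted variable that must enter most analyses, Clinical Center, and does not name schedule.

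Several stronger readings are tempting, and the documents do not support them.

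- *All of Questions 1, 9 and 10 are biased.* Question 10 concerns change over time, which is not biased (step 4). Prevalence at a visit both schedules share does not depend on how often subjects are tested.
- *Symptoms are inflated 1.5-fold because history is 3-monthly against 6-monthly.* That figure requires symptoms to be recorded only if present on a visit day. Sections 7.2.1 and 7.2.4 instruct every subject to contact the centre when trigger symptoms occur, and the evaluation follows the same rule in all groups.
- *2.5 is the expected inflation.* It is the extreme of the range: a silent finding lasting at most 3 months and seen only on scheduled films. Symptom-evaluation and one-month follow-up films exist in every group and reduce the difference.
- *Section 4 commits the study to concluding that HIV damages the lung.* It speaks of an excess in prevalence, offers HIV causation as one inference, and treats it as grounds for a further study.
- *The PCP contrast is a surveillance artefact.* With 0% PCP assumed in Group C, unequal testing cannot create that contrast.
- *Seroconverters in Group C make the net direction unknowable.* The sentence on original assignment can be read as keeping them among the seronegatives, but the listed predictor in Questions 9 and 10 is HIV status, which 6-monthly antibody tests can update. The protocol gives no seroconversion rate, so no size can be attached.

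**Conclusion.** The concern holds in a limited form. Carried out as written, the plan can produce a seropositive excess from surveillance alone in two places: incidence or ever-found measures of silent or transient film and lung-function abnormalities (Question 9, secondary objective 3), and disease detected only through a scheduled film (Question 1 association rule).

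The mechanism follows from the protocol's own schedules. The size does not, because neither the per-test probability nor the duration of findings is given. The ratio runs from 2.5 for findings lasting up to 3 months down to 1.0 for those lasting 12 months or more. Under the independent-test assumption, a 1% per-test probability gives 7.2% against 3.0% over three years. Disease presenting through symptoms is little affected; rates of decline and common-visit prevalence are not affected. The handling of seroconverters is a secondary point of unknown size. The point is worth settling before analysis because the correction is specific and cheap.

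**What to change.** Change the analysis wording in Appendix 1; no visit or test changes.

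- **Film and lung-function findings, seropositive versus Group C:** count only results from visits common to both schedules (months 0, 12, 24 and 36; 6-monthly for history items), keeping all seropositives. This costs little.
- **Disease incidence that scheduled films can trigger (Question 1):** make A-1 plus B-1 versus C the HIV-association comparison, or report it beside the pooled one. Restriction widens intervals by about 7–13% for equal-variance outcomes such as DLCO, but by about 41% for PCP in A or B versus C. That price is a reason to keep the pooled PCP estimate alongside.
- **Seroconverters:** in these comparisons, censor Group C subjects at their first positive HIV antibody test, using the 6-monthly tests already scheduled. Keep analysis by original assignment for the randomised intensive-versus-routine substudy.

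Question 10 needs no change on this account.
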